	
past 14 days, including:
 
a. Liver function tests (LFTs) such as albumin, direct bilirubin, total bilirubin, aspartate aminotransferase (AST), and alanine aminotransferase (ALT) ≥ 3 times the upper limit of normal (ULN).b. The investigator may deem the subject eligible if in the opinion of the investigator, the clinically significant abnormal laboratory values are deemed to be acceptable and to not have an impact on subject safety. 
5. Inadequate supervision by parent(s)/caregiver(s).
 
6. For appropriate subjects, an affirmative answer to queries regarding active suicidal ideation with some intent to act but without a specific plan or active suicidal ideation with specific plan and intent on the C-SSRS assessment at the Screening Visit. Subjects who have significant findings for suicidal ideation as assessed by the C-SSRS must be referred to the Investigator for follow-up evaluation.

Test product, dose and mode of administration:	
Cannabidiol Oral Solution: an oral solution containing pharmaceutical grade cannabidiol (nonplant-based).
 
Subjects who completed INS011-14-029 will initiate this study on the dose with which they were being treated previously (10, 20, or 40 mg/kg/day administered in twice daily doses of 5, 10, or 20 mg/kg, depending on dose cohort). For subjects enrolling from INS011-15-054 their dose will be the same as in the previous study (maximum of 40mg/kg/day). The total daily dose (mg/kg/day) will be administered in two equal concentration doses (mg/kg) at 12-hour intervals.
 
Dosing of the investigational product may be adjusted at any time based on investigators discretion, however maximum daily dose will not exceed 40 mg/kg/day.
 
Subjects who will not continue to receive Cannabidiol Oral Solution under the Investigator IND Expanded Access Program may be tapered off based on Investigator's preference and subject's tolerability. The investigator should ensure that the taper is planned in advance to allow sufficient time to complete the taper prior to Visit 10 at 48 weeks (± 10 days). The date of entering the Expanded Access Program will be documented in the EDC. The timing of administration of the drug with regards to food should be consistent throughout the duration of the study.

Reference therapy, dose, and mode of administration:	Not applicable.

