4.1.1 Dose Adjustments

IP dose may be adjusted at the investigators discretion. Dose may be adjusted up or down based on efficacy, safety or tolerability. All dose changes must be clearly documented in the eCRF. Maximum dose must never exceed 40mg/kg/day.

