6.1.1.1 Monitoring of AEs Potentially Related to Drug Metabolism

Cannabidiol inhibits drug metabolism mediated by a subset of CYP proteins (see Section 1.1.2). Thus, the Investigator and study center staff should monitor subjects who are taking concomitant medications that are metabolized by CYP2C19, CYP2C9, or CYP1A1 or by p-glycoprotein with special care. Medication(s) that is/are inhibitor(s) or inducer(s) or sensitive substrates of CYP3A4 should be monitored with special care.

The CYP proteins noted above metabolize a selection of clinically important AEDs. As such, subjects should be monitored for AEs that may be related to a change in the metabolism of background AEDs. These may include:

- Increases in liver enzymes
- Increases in side effects associated with background AEDs
- Development of new side effects associated with background AEDs.

Similarly, several AEDs are known inducers of CYP3A4.²⁴ As such, their use may result in alterations in the level of the investigational product. Plasma levels of cannabidiol and 7-OH cannabidiol will be assessed as described in Section 6.2.

The Investigator may choose to assess plasma levels of background AEDs with which the subject is being treated should AEs arise that may be due to altered metabolism of these medications (see above). As noted in Section 4.3, decisions to alter background AED medications and dosing due to safety concerns will be considered on a case by case basis.

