Concentration data of CBD and 7-OH-CBD will be tabulated and summarized by CBD dose level (based on the daily dosing regimen, mg/kg/day, of CBD when the plasma sample is taken) at each collection time (scheduled week) using descriptive statistics (n, mean, SD, minimum, median, maximum, and percent coefficient of variation). In addition, dose-normalized concentrations of CBD and 7-OH-CBD will be tabulated and summarized by clobazam flag

Pharmacokinetic Statistical Analysis Plan
Insy Clinical Trial Protocol INS011-14-030

(yes/no) at each collection time (scheduled week) using descriptive statistics. CBD and 7-OH-CBD concentration-time data for subjects continuing on study medication as part of the Expanded Access Program will be summarized in a secondary set of tables and figures.

Concentration data of clobazam and norclobazam will be stratified by clobazam flag (yes/no), tabulated, and summarized using descriptive statistics.

In the data tabulation and summarization, concentrations below the lower limit of quantitation (BLQ) will be set to zero.

Plots of mean concentration-time for CBD and 7-OH-CBD and dose-normalized CBD and 7-OH-CBD will be created by CBD dose level, with and without stratification by clobazam (yes/no). Plots of concentration-time data for CBD and 7-OH-CBD for individual subjects will be created; since the dose level may vary during the study, the dose level at a given sample time will be labeled or foot-noted (if possible) in the figure. Plots for clobazam and norclobazam will be stratified by subjects on clobazam therapy (yes/no).

Pharmacokinetic Calculations

The metabolite-to-parent ratio (MRCtrough) will be calculated using concentrations of 7-OH CBD (metabolite) and CBD (parent) at each Visit, starting with the first trough sample obtained and through the remaining visits. If either CBD or 7-OH CBD concentration is not reportable or BLQ, MRCtrough will be reported as "not applicable". MRCtrough for clobazam will be calculated using the same methodology.

To assess the degree of accumulation during long-term BID administration of cannabidiol oral solution after 1 month treatment (Visit 5), an accumulation ratio (RCtrough) will be estimated using the dose-normalized trough plasma concentrations of CBD and 7-OH-CBD at each Visit, according to:

$$RCtrough = \text{Conc}/D(n^{\text{th}} \text{ visit dose})/\text{Conc}/D(5^{\text{th}} \text{ visit dose}),$$

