where $\text{Conc}/D(n^{\text{th}} \text{ visit dose})$ is the dose-normalized trough concentration at a given Visit beyond 1 month (i.e., n^{th}) and $\text{Conc}/D(5^{\text{th}} \text{ visit dose})$ is the dose-normalized trough concentration determined at Visit 5 (scheduled on Week 4). If either $\text{Conc}/D(n^{\text{th}} \text{ visit dose})$ or $\text{Conc}/D(5^{\text{th}} \text{ visit dose})$ is not reportable or BLQ, RCtrough will be reported as "not applicable".

RCtrough and MRCtrough will be tabulated and summarized by CBD dose level (based on the daily dosing regimen, mg/kg/day, of CBD when the plasma sample is taken) at each collection time (week) using descriptive statistics (n, mean, SD, minimum, median, maximum, and percent coefficient of variation). MRCtrough for clobazam will be stratified by clobazam flag (yes/no), tabulated, and summarized using descriptive statistics.

[REDACTED]

Page 8 of 12

Pharmacokinetic Statistical Analysis Plan
Insy Clinical Trial Protocol INS011-14-030

REPORTING

The pharmacokinetic tables and figures described in this PK SAP will be presented in the listings section of the clinical study report (CSR) for INS011-14-030. Appropriate numbering to be provided by the medical writer.

GENERAL REFERENCES

- “Guidance For Industry: Statistical Approaches to Establishing Bioequivalence” U.S. Department of Health and Human Services Food and Drug Administration Center for Drug Evaluation and Research (CDER) January 2001.
- “Guidance For Industry: Bioavailability and Bioequivalence Studies for Orally Administered Drug Products-General Considerations” U.S. Department of Health and Human Services Food and Drug Administration Center for Drug Evaluation and Research (CDER) March 2003.
- “Guidance For Industry: Food-Effect Bioavailability and Fed Bioequivalence Studies” U.S. Department of Health and Human Services Food and Drug Administration Center for Drug Evaluation and Research (CDER) December 2002.
- “Guidance For Industry: Drug Interaction Studies – Study Design, Data Analysis, Implications for Dosing, and Labeling Recommendations” U.S. Department of Health and Human Services Food and Drug Administration Center for Drug Evaluation and Research (CDER) February 2012.

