- Brian P. Smith, Francois R. Vandenbende, Karl A. DeSante, Nagy A. Farid, Pamela A. Welch, John T. Callaghan, and S. Thomas Forgue, “Confidence Interval Criteria for Assessment of Dose Proportionality”, *Pharmaceutical Research*, Vol. 17, No. 10, 2000; p.1278-1283.

[REDACTED]

Page 9 of 12

Pharmacokinetic Statistical Analysis Plan
Insy Clinical Trial Protocol INS011-14-030

EXAMPLE TABLES AND FIGURES

Concentration listing with descriptive statistics

Analyte	CBD_Dose (mg/kg)	Subject_ID	Subject_Alias	Visit						
				2	5	6	7	8	9	10
Cannabidiol	5.00	xxx	xxx							
				n						
				Mean						
				SD						
				Min						
				Median						
				Max						
				CV%						

Similar format for each analyte, dose level, and for dose-normalized concentrations

Concentration summary table

Analyte		Visit 2			Visit 5
		Concentration (ng/mL)	DN_Concentration (ng/mL/mg/kg)	CBD_Dose (mg/kg)	
Cannabidiol	n Mean SD Min Median Max CV% Geometric Mean				

[figure not shown]
Similar table for 7-OH CBD

[REDACTED]

Page 10 of 12

Pharmacokinetic Statistical Analysis Plan
Insys Clinical Trial Protocol INS011-14-030

Mean Figures

Similar format for all figures

Page 11 of 12

Pharmacokinetic Statistical Analysis Plan Insys Clinical Trial Protocol INS011-14-030

MRCthrough table

			Visit							
			2	5	6	7	8	9	10	
CBD_Dose (mg/kg)	Subject_ID	Subject_Alias	MRCTrough_CBD							
5.00	xxx	xxx								
			n							
			Mean							
			SD							
			Min							
			Median							
			Max							
			CV%							

RCTrough table

				Visit				
				6	7	8	9	10
Analyte	CBD_Dose (mg/kg)	Subject_ID	Subject_Alias	RCTrough				
Cannabidiol	5.00	xxx	xxx					
				n				
				Mean				
				SD				
				Min				
				Median				
				Max				
				CV%				

[REDACTED]
Page 12 of 12Pharmacokinetic Statistical Analysis Plan
Insys Clinical Trial Protocol INS011-14-030

Concentration listing

Analyte	Subject ID	Subject Alias	Visit	Week	CBD Daily Dose (mg/kg/day)	Prior Visit CBD Dose (mg/kg)	Clobazam Dose (mg)	Route Of Clobazam	Dose Frequency Of Clobazam	Conc (ng/mL)
CBD	xxx	xxx	5	4	20.00	10.00	10.00	ORAL	QD	xxx
CBD	xxx	xxx	6	8	20.00	10.00	10.00	ORAL	QD	xxx
CBD	xxx	xxx	7	12	20.00	10.00	10.00	ORAL	QD	xxx

Note: This listing will be based on the analysis data set provided by the statistician or biostatistics group.

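### For subjects whose dose differs from the Visit 5 dose, RCtrough equals accumulation only under dose proportionality, and the pooled clobazam table has a related weakness

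*SAP*

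**What the plan says.** The PK SAP (Pharmacokinetic Calculations) says that "an accumulation ratio (RCtrough) will be estimated using the dose-normalized trough plasma concentrations of CBD and 7-OH-CBD at each Visit". Each trough is divided by its dose, and the result is divided by the same quantity at Visit 5 (Week 4). RCtrough is then summarised at each week by the mg/kg/day dose in force when the sample was drawn. The example RCtrough table runs from Visit 6 to Visit 10.

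Under Concentration-Time Data Tabulation, "dose-normalized concentrations of CBD and 7-OH-CBD will be tabulated and summarized by clobazam flag" (yes/no) at each scheduled week. No dose stratum is named for that table. Clobazam is the only co-medication used as a stratifier.

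Doses are not fixed. Subjects from INS011-14-029 start on "10, 20, or 40 mg/kg/day administered in twice daily doses" (Protocol Synopsis, Test product), and Protocol 4.1.1 says "Dose may be adjusted up or down based on efficacy, safety or tolerability". Protocol 4.1.2 allows a taper, to be finished before Visit 10. Section 3.3 of the main SAP drops by-dose presentation because investigators may titrate to any dose.

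Protocol 4.3 allows AEDs to be started, stopped or adjusted throughout. Protocol 6.1.1.1 says of CYP3A4-inducing AEDs: "As such, their use may result in alterations in the level of the investigational product".

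The PK SAP describes no proportionality analysis. The topic appears only as a title under General References, "Confidence Interval Criteria for Assessment of Dose Proportionality".

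**The concern.** Dividing a trough by its dose removes the effect of a dose change only when trough is proportional to dose. Otherwise a titrated subject's RCtrough combines any accumulation with the curvature of the dose-concentration relation. Stratifying by current dose does not separate the two: a subject moved from 10 to 40 mg/kg/day sits in the 40 stratum beside subjects who were on 40 at Visit 5.

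The documents give some reason not to take linearity for granted. Protocol 1.4 says cannabidiol is cleared mainly by CYP3A4 and CYP2C19 and may inhibit both. Section 14 of the main SAP lists a PK result as a possible reason for a dose modification, so changed-dose pairs may be partly selected on concentration.

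Change in plasma levels over long-term treatment is a stated objective (Protocol 2.1; SAP 2.2), and RCtrough is the only accumulation measure planned. What is at stake is how its departures from 1 are read.

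The clobazam table compares dose-normalised levels across all doses. If users and non-users are on different doses, a non-proportional relation can look like an interaction.

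**Working it through.** The plan states no expected RCtrough, exponent or sample size for this point, so there is no figure to reproduce. The calculations below are illustrations with true accumulation set to 1.

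**Inputs from the documents.** The RCtrough definition and its Visit 5 reference (PK SAP); doses of 10, 20 and 40 mg/kg/day (Protocol Synopsis); half-life range of 18 to 33 h (Protocol 1.1.4.1; other formulations, intravenous or inhaled).

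**Assumed, not in the documents.** Dose exponent b of 0.7 to 1.3; clearance factor k of 1.25 to 2.0 for an inducer; illustrative dose and inducer mixes by clobazam use.

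**1. Dose change.** With trough C = a·D^b,

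RCtrough = (a·Dn^b / Dn) / (a·D5^b / D5) = (Dn/D5)^(b−1).

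| Dose at Visit 5 → visit n (mg/kg/day) | b = 0.7 | b = 0.8 | b = 1.0 | b = 1.2 | b = 1.3 |
|---|---|---|---|---|---|
| unchanged | 1.00 | 1.00 | 1.00 | 1.00 | 1.00 |
| 10 → 20 | 0.81 | 0.87 | 1.00 | 1.15 | 1.23 |
| 10 → 40 | 0.66 | 0.76 | 1.00 | 1.32 | 1.52 |
| 40 → 20 | 1.23 | 1.15 | 1.00 | 0.87 | 0.81 |

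For example, 4^(−0.3) = 0.66 and 4^0.3 = 1.52.

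**2. What a stable subject should show.** Five half-lives are 5 × 18/24 = 3.75 days to 5 × 33/24 = 6.88 days, well inside 28 days. If those half-lives apply here, RCtrough should be near 1 under a stable dose and stable AEDs. The artefacts in step 1 could then be as large as any departure the table is meant to detect.

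**3. Recent dose change, b = 1.** For 40 → 20 mg/kg/day sampled t hours later, assuming a mono-exponential approach to the new steady state, RCtrough = [20 + 20·2^(−t/t½)]/20. At 48 h this is 1.16 (t½ 18 h) to 1.36 (33 h). At 7 days it is 1.00 to 1.03. A recent change therefore distorts the ratio even under exact proportionality.

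**4. Clobazam table, no true interaction.** Suppose users are on 10/20/40 mg/kg/day in shares 20/30/50% and non-users in shares 50/30/20%. The ratio of mean C/D, yes to no, is Σw·D^(b−1) for users divided by the same sum for non-users:
- b = 0.7: 0.388/0.439 = 0.88
- b = 1.3: 2.648/2.339 = 1.13

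**5. Inducing AEDs, a separate mechanism.** At constant dose with b = 1, multiplying clearance by k gives RCtrough = 1/k when an inducer is started and k when it is stopped. For k = 1.25, 1.5 and 2.0 that is 0.80, 0.67, 0.50 and 1.25, 1.50, 2.00. In the clobazam table, inducer use of 10% in users against 40% in non-users gives (0.1/k + 0.9)/(0.4/k + 0.6): 1.07 at k = 1.25 and 1.19 at k = 2.0.

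**The case against.** The plan already offers partial protection:
- Raw concentrations and RCtrough are summarised by dose level at sampling.
- The example tables extend the by-dose layout to dose-normalised concentrations, which allows an informal look at whether C/D is flat across doses.
- Mean dose-normalised plots are made by dose level, with and without clobazam stratification, so a within-dose clobazam view exists as figures.
- Listings give the dose with each sample, and individual plots are to show it where possible, so dose changers can be identified.
- Protocol 8.3.5 leaves open a population PK model under its own SAP.

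All of this stands, but none of the planned summaries separates changed-dose from stable-dose pairs in RCtrough, and the population model is optional.

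The exponent is also assumed, 10 to 40 is the widest move among the INS011-14-029 starting doses, and the documents do not say how many subjects change dose after Visit 5. No test or decision rule uses RCtrough (SAP 6.5), and the PK outputs go to the listings section of the study report. These points limit the weight of the concern without removing it.

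A reader might infer that proportionality has never been examined for this product. The documents do not support that. INS011-14-029 was a PK study of the product (Protocol 1.1.5) and used these doses, but its results are not available here. All that can be said is that this PK SAP plans no assessment.

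**Conclusion.** The point holds in a limited form. Where the mg/kg/day dose differs between Visit 5 and visit n, RCtrough can be read as accumulation only if trough is proportional to dose, and the planned strata do not keep those pairs apart. Under the assumed exponents the artefact is 0.66 to 1.52 for a 10-to-40 change and 0.81 to 1.23 for a doubling; it is nil at an unchanged dose. The pooled clobazam table shares the weakness only if dose mix differs by clobazam use, and the planned stratified plots partly cover it. MRCtrough is a ratio within one sample and is not affected by dose normalisation.

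Two stronger readings are tempting and should be resisted. First, the effect of inducing AEDs does not follow from dose normalisation: it arises at constant dose under exact proportionality, a proportionality test would not cure it, and only stopping an inducer mimics accumulation, since starting one lowers the ratio. Second, changed-dose pairs are not worthless: they remain valid if proportionality and clearance hold and the new steady state has been reached.

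The true size cannot be derived from the documents. This is a worthwhile, inexpensive improvement to a descriptive analysis.

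**What to change.** In the PK SAP:
- Report RCtrough separately for pairs whose mg/kg/day dose equals the Visit 5 dose, which is the summary to read as accumulation, and for changed-dose pairs. Footnote that the latter also depend on dose proportionality.
- Flag pairs with an inducing AED started or stopped since Visit 5, using a pre-specified AED list. Show the unchanged-dose summary with and without them.
- Tabulate the clobazam comparison within dose level as well as pooled.
- Keep a summary of all pairs. Dose is changed for efficacy, safety or tolerability, so the unchanged-dose subset is selected after Visit 5.

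The dose at each sample and the AED records are already collected, so no new data are needed. The costs are smaller cells, an AED list to define (the documents contain none) and its application to start and stop dates.

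Separately, the PK SAP's Study Design text mentions only dose reduction, whereas Protocol 4.1.1 allows adjustment in both directions. These passages must be reconciled.

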Physical examination and neurological examination ^k	X	X				X		X	X
Dispense (D), review (R), and collect (C) subject seizure and dosing diary ^l					D	D/R/C		R/C	
Dispense (D) and collect (C) study drug and review (R) dosing procedures		D/R	D/R/C	D/R/C	D/R/C	D/R/C		C	
Administer morning dose of study drug in the clinic		X				X			
AEs and SAEs	X	X	X	X	X	X		X	X
Blood draw for plasma levels		X			X	X		X	X

Assessments ^a	Visit 1 (14 Day Screening Period ^b)	Treatment Period						Final Visit / Discontinuation Visit ^d (Visit 10) Week 48 ±10 days ^e (if not conducted at a normally scheduled visit)	Follow-up Visit Two weeks after Final Visit / Discontinuation Visit (Visit 11) ±5 days
		Visit 2 (Day 1 ^c)	Visit 3 (Week 1) ±3 days	Visit 4 (Week 2) ±3 days	Visits 5, 6, & 7 Monthly: (Weeks 4, 8 & 12) ±7 days	Visits 8, 9, Quarterly: (Weeks 24 and 36) ±10 days ^d			
Investigator and Parent(s)/caregiver(s) CGI-S ^m	X	X			X	X		X	X
Investigator and Parent(s)/caregiver(s) CGI-I ^m					X	X		X	X
IPES ^{n, o}		X			X	X		X	X
VABS ^{n, p}		X						X	
C-SSRS ^q	X	X			X	X		X	X
Reminders for next visit ^s	X	X	X	X	X	X			

^a At Visits 2, 5, 6, 7, 8, 9 and 10 all assessments are to precede administration of the morning dose of the investigational product (i.e., the subject should arrive for their study visit without having taken the morning dose of the investigational product). See Section 5.1 for more details.

^b A Screening Period (Visit 1) will be required only for all subjects that do not rollover within 14 days of completing their previous study.

^c Visit 2 (Day 1) may occur simultaneously with Day 11 from INS011-014-029 or within 14 days of Visit 1 (Screening Visit) for INS011-14-030. All assessments (except vital signs) completed within 14 days prior to administration of the first dose of Cannabidiol Oral Solution in INS011-14-030 may be used for Visit 2 (Day 1) (to avoid repetition of procedures).

^d Subjects will receive two daily oral doses of Cannabidiol Oral Solution for approximately 48 weeks or until the investigational product is successfully approved for marketing in the US (whichever occurs earlier), inclusive of their treatment on the previous

study, unless they are discontinued due to a reason described in Section 3.4.3. After 12 weeks, study visits will be completed at a quarterly frequency; the definition of quarterly is every 12 weeks (e.g., Weeks 24 and 36).

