^r The Investigator or study center staff will remind the subject and/or parent(s)/caregiver(s) that the subject should not take the morning dose of the investigational product prior to assessments/clinic visit on the date of their quarterly study visits. The last dose of the investigational product prior to quarterly visits should be administered in the evening the day immediately prior. The subject and/or parents(s)/caregiver(s) will also be reminded that the date and time of the evening meal on the day prior to the quarterly study visits should be recorded in the subject seizure and dosing diary.

AE: adverse event; AED: antiepileptic drug; CGI-I: Clinical Global Impression of Improvement; CGI-S: Clinical Global Impression of Severity; C-SSRS: Columbia-Suicide Severity Rating Scale; ECG: electrocardiogram; eCRF: electronic case report form; ICF: informed consent form; IPES: Impact of Pediatric Epilepsy Scale; SAE: serious adverse event; VABS: Vineland Adaptive Behavior Scales, Second Edition – Survey Interview Form including the Maladaptive Behavior Index (VABS)

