5.2 Treatment Period

Subjects that completed INS011-14-029 will complete this study through the 48 week visit, unless they are discontinued due to a reason described in Section 3.4.3, or until the investigational product is successfully approved for marketing in the US (whichever occurs earlier). For subjects that participated in INS011-15-054 will participate through the Week 48 visit unless they are discontinued due to a reason described in Section 3.4.3, or until the investigational product is successfully approved for marketing in the US (whichever occurs earlier); however, the combined treatment duration in INS011-14-030 and INS011-15-054 will not exceed approximately 48 weeks

At Visits 2, 8, and 9, all assessments are to precede administration of the morning dose of the investigational product. Specifically, the subject will NOT receive the investigational product on the morning of Visits 2, 8, and 9 UNTIL all assessments have been completed. The morning dose of the investigational product should be administered following completion of all assessments.

Given the timing of study assessments in regards to administration of the investigational product and the twice daily dosing of this medication, all visits requiring in-clinic dose administration will preferably be scheduled in the morning. Ideally, all assessments should be completed before 12 PM (noon) in the time zone of the study center to adhere as closely as possible to the 12-hour interval for dosing (see Section 4.6).

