5.2.2 Visits 3 and 4 (Weeks 1 and 2) ±3 days

The following procedures will be completed:

- Record concomitant medications and concomitant procedures.
- Record vital signs (blood pressure, heart rate, respiratory rate, and temperature measurements).
- Record recent medication history including current AEDs, vitamins, herbal preparations, blood products, and over-the-counter drugs.
- Dispense and collect investigational product.
- Review of dosing procedures for the investigational product.
- Record AEs and SAEs.
- Remind subject/parent(s)/caregiver(s) of next scheduled visit.

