6.2 Plasma Levels

Whole blood will be obtained in a Vacutainer® containing heparin anticoagulant for the determination of the plasma levels of cannabidiol and 7-OH cannabidiol in human plasma. The sample will be obtained as indicated in Table 1 prior to daily study medication dosing on that day. Samples for plasma level assessment of cannabidiol and 7-OH cannabidiol should

be collected immediately prior to administration of the morning dose of the investigational product on indicated days.

The following information will be captured for blood sample collection in each subject's eCRF:

- Subject number and initials
- Time and date of most recent administration of the investigational product prior to the sample collected for plasma level analysis
- Time and date of each blood sample collected for plasma level analysis
- Time and date of subject's ingestion of food (i.e., the evening meal on the day prior to each study visit).

Samples for the determination of the investigational product in human plasma will be analyzed by the Sponsor, using an appropriate bioanalytical method. It is anticipated that this will include estimates of concentration and trough (steady state) concentration of cannabidiol and 7-OH cannabidiol (monthly to quarterly). For subjects taking clobazam, levels of clobazam and its major metabolite (norclobazam) will be measured if there are safety concerns.

The analytical method for human plasma will be developed and validated. All samples still within the known stability of the investigational product will be analyzed.

Exploratory plasma samples will be shipped to the Sponsor or the Sponsor-designated bioanalytical laboratory.

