- Subjects who completed INS011-14-024 and INS011-14-025 will continue treatment with the dose at which they were being treated previously, unless tolerability issues were observed for a particular subject. This dose will be that deemed safe and tolerable in INS011-014-029.

The planned dosing regimen is twice daily administration (BID).

[REDACTED]

Page 5 of 12

Pharmacokinetic Statistical Analysis Plan
Insy Clinical Trial Protocol INS011-14-030

Dosing of the investigational product may be reduced for an individual subject as per Investigator opinion should tolerability issues arise. Treatment with established antiepileptic drugs (AEDs) will continue without interruption and changes will be permitted as necessary based on safety concerns of changes in seizure control.

Visits will be scheduled at 1 week, 2 weeks, and monthly for the first 3 months after completion of the subject's prior study, and quarterly thereafter. All subjects will complete a Final Visit/Discontinuation Visit regardless of when they stop treatment/complete the study. A Follow-up Visit will occur 2 weeks after the Final Visit/Discontinuation Visit.

At each visit, a record of the incidence and severity of AEs, treatment-emergent AEs (TEAEs), and SAEs will be collected and this will serve as a primary outcome criterion for this study. Other safety-related parameters such as 12-lead ECG and hematology, chemistry, and urinary analyses will also be assessed at each visit except the 2-week visit.

At each visit except the 1- and 2-week visits, the following qualitative assessments will be completed: Clinical Global Impression of Improvement (CGI-I), Clinical Global Impression of Severity (CGI-S), Child Behavior Checklist (CBCL) Total Problems scale, Impact of Pediatric Epilepsy Scale (IPES), Vineland Adaptive Behavior Scales (VABS), Vineland Maladaptive Behavior Scales (VMBS), and Columbia-Suicide Severity Rating Scale (C-SSRS).

Seizure diaries will be reviewed to assess control of seizures (frequency, duration, and severity) throughout the duration of the study.

Collection of Pharmacokinetic Samples

Determination of trough (pre-dose) plasma levels of cannabidiol (CBD) and its 7-OH metabolite (7-OH-CBD) will be performed. Samples for assessment of CBD and 7-OH CBD trough plasma levels will be collected immediately prior to administration of the morning dose of the investigational product at the following times:

- Visit 2 (Day 1, Week 0)
- Visit 5 (Week 4)
- Visit 6 (Week 8)

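### The hold-dose instructions do not reach Visit 5, the denominator of RCtrough, and the PK SAP does not say what to do with a sample taken after the dose or after a taper

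*SAP*

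**What the plan says.** **The pre-dose requirement covers Visit 5 in three places.**
- Protocol Table 1, footnote a: "At Visits 2, 5, 6, 7, 8, 9 and 10 all assessments are to precede administration of the morning dose of the investigational product". It adds that the subject should arrive undosed.
- Protocol Section 6.2: plasma samples should "be collected immediately prior to administration of the morning dose of the investigational product on indicated days".
- PK SAP, Collection of Pharmacokinetic Samples: "trough plasma levels will be collected immediately prior to administration of the morning dose of the investigational product". The visit list that follows includes Visit 5.

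**The operating text is narrower.**
- Section 5.2: "the subject will NOT receive the investigational product on the morning of Visits 2, 8, and 9 UNTIL all assessments have been completed". Visits 5, 6, 7 and 10 are not named.
- Table 1 footnote r: families are told the subject "should not take the morning dose of the investigational product prior to assessments/clinic visit on the date of their quarterly study visits". Visit 5 is a monthly visit.
- Section 5.2.2, the last reminder before Visit 5, says only: "Remind subject/parent(s)/caregiver(s) of next scheduled visit". Section 5.2.3, which precedes Visits 6 and 7, is equally bare and lists the plasma draw with no pre-dose condition. Section 5.2.5 (Visits 8 and 9) does spell out the held dose.

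**The calculation.** RCtrough is the dose-normalized trough at a later visit divided by that at Visit 5. In the PK SAP, Pharmacokinetic Calculations, the denominator "is the dose-normalized trough concentration determined at Visit 5 (scheduled on Week 4". It is set to not applicable only if either value is not reportable or BLQ. The table shell runs from Visit 6 to Visit 10. Planned statistics are n, mean, SD, minimum, median, maximum and CV%. Dose and sample times are captured in the eCRF, but no rule uses them to accept or reject a sample.

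**The concern.** RCtrough is the PK SAP's named within-subject measure of accumulation, and monitoring plasma levels over time is a stated objective. One Visit 5 value sits under every later ratio for that subject. If a family gives the usual morning dose before the Week 4 visit, the level drawn is not a trough, yet nothing in the calculation removes it. The error has one direction: the denominator is too high, so later pre-dose visits look lower than they should and accumulation can be hidden. Later visits are also better protected, because the explicit hold-dose text applies to Visits 8 and 9 and, through the Visit 9 reminder, to Visit 10.

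Two smaller gaps sit in the same table. Under Section 4.1.2, subjects not entering Expanded Access may complete a taper before Visit 10, so a Visit 10 level may be off drug. And the arithmetic mean of a ratio is above 1 even when nothing changes.

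**Working it through.** The documents give no RCtrough value to reproduce, so the sizes below are illustrations.

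**Inputs from the protocol.** Dosing interval 12 h (synopsis). Cannabidiol half-life 24 h intravenous and 31 h inhaled (Section 1.1.4.1). Dronabinol half-life 5.5 h, cited to support twice-daily dosing (Section 4.1). None is for this product.

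**Assumed.** One compartment at steady state, first-order absorption with ka 0.3 to 1.5 per h, Visit 5 drawn 1 to 4 h after the dose, later samples true 12 h troughs, within-subject CV 30%.

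**Step 1: one subject, no true change.** With k = ln 2 / half-life, the level at time t is proportional to

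f(t) = e^(−kt)/(1 − e^(−12k)) − e^(−ka·t)/(1 − e^(−12ka)),

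and RCtrough = f(12)/f(t).

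- 24 h, ka 1.5, t = 2: f(2) = 3.223 − 0.050 = 3.173; f(12) = 2.414; ratio 2.414/3.173 = 0.76.
- 31 h, ka 0.3, t = 1: f(1) = 4.155 − 0.762 = 3.394; f(12) = 3.221; ratio 3.221/3.394 = 0.95.

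These are the ends of the range: 0.76 to 0.95 at 24 to 31 h. At 5.5 h the range is 0.30 to 0.69.

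**Step 2: group.** If a share p of Visit 5 samples is post-dose with factor f, the geometric mean ratio is f^p.

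| p | f = 0.95 | f = 0.76 |
|---|---|---|
| 10% | 0.995 | 0.973 |
| 25% | 0.987 | 0.934 |

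Simulated medians agree to within 0.001. At 5.5 h the simulated median is 0.94 to 0.97 (10%) or 0.84 to 0.92 (25%).

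**Step 3: sampling error for scale.** SD of the log ratio = √(2 ln 1.09) = 0.415. The 95% range of the geometric mean ratio, exp(±1.96 × 0.415/√n), is 0.83 to 1.20 for n = 20 and 0.90 to 1.11 for n = 60. Those n are the source-study maxima. The planned tables split by dose level, so the actual ranges are wider.

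**Step 4: arithmetic mean with every sample correct.** For independent lognormal X and Y with equal CV, E[X/Y] = 1 + CV²: 1 + 0.30² = 1.09, and 1 + 0.50² = 1.25. The median and geometric mean are 1.00.

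**Step 5: Visit 10.** If D is the dose at the visit and the taper is complete, D = 0 and the ratio is undefined. If D is the most recent dose taken, an off-drug level is normalized to it, and each further 24 to 31 h off drug halves the value. The PK SAP does not say which applies.

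**The case against.** A reader might infer that the plan has no timing rule for Visit 5, or that Section 5.2 lets families dose first. The documents do not support either. The pre-dose rule is stated three times, footnote a itself says to arrive undosed, and RCtrough is defined on troughs. Section 5.2 names the visits with in-clinic dosing in Table 1, so its silence on Visit 5 permits nothing. What stands is narrower: the instruction is not repeated where staff and families would meet it, and the calculation has no rule for a sample that breaks it.

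On Visit 10, the PK SAP tabulates RCtrough by the regimen in force when the sample is taken. A fully tapered subject would not fit an active-dose row, and an undefined or BLQ value becomes not applicable. That covers part of the case. A quantifiable level normalized to the last dose is still not ruled out, because D is undefined. The separate Expanded Access tables are described for concentration-time data, not for RCtrough.

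The PK SAP already plans to list actual time post dose where available, so some mistimed samples would be visible. The example listing has no such column, however, and listing a sample does not remove it from the summary.

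It is also fair that the larger effects rest on dronabinol, a different compound. Visits 6 and 7 share the reminder gap, so a family's habit of dosing first would partly cancel there. The planned median already avoids the bias of the arithmetic mean.

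Finally, a 95% confidence interval for RCtrough might seem already promised by the synopsis. It is not: the synopsis gives concentrations their own list of statistics, without an interval.

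**Conclusion.** The point holds as a minor clarification to descriptive PK. The hold-dose instructions are inconsistent for Visits 5 to 7, and a post-dose Visit 5 sample would enter RCtrough as a trough. For one affected subject the ratio would be 0.76 to 0.95 with no true change at the cited cannabidiol half-lives. At group level with 10% mistimed it would be about 0.97 to 0.995, well inside sampling error.

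It would go too far to say that accumulation will be masked. The mistimed share is unknown, and draw times, absorption rates and CV are assumed. RCtrough supports no inference, and dose-normalized concentrations by visit are also planned, though with the same timing gap. No safety conclusion turns on this point.

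**What to change.** 1. **Protocol.** Align Section 5.2, footnote r and the reminders given before Visits 5 to 7 (Sections 5.2.2 and 5.2.3) with footnote a. This helps only visits still to come.
2. **PK SAP, samples.** Use the captured dose and sample times to keep samples taken after that morning's dose out of the trough, RCtrough and MRCtrough summaries, and list them with time post dose. Keep not applicable for subjects with no valid Visit 5 trough.
3. **PK SAP, dose.** State which dose D is, and leave post-taper Visit 10 samples out of RCtrough.
4. **PK SAP, statistics.** Add the geometric mean to the RCtrough table, as the concentration summary shell already does.

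A time-since-dose window is optional. Because the protocol says "Ideally, all assessments should be completed before 12 PM (noon) in the time zone of the study center", 10 to 16 h may look natural, but two accepted samples at its opposite ends would give ratios of 2^(−6/24) = 0.84 to 2^(6/24) = 1.19 at a 24 h half-life. That is comparable in size to the error being removed. Any window should be narrower or left to the pharmacokineticist.

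The cost is a protocol clarification and a few lines in the PK SAP, with no new data. A few mistimed samples leave the summaries. At Visits 5 to 7 the recorded last-dose time cannot be checked against a diary, because the dosing diary covers only the week before Visits 8, 9 and 10 (Section 6.3.2).
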